# **STUDY SYNOPSIS**

Title of Study:	Effect of Magnesium and Thiamine on red cell	
	transketolase activity	
Study Centre:	Glasgow Royal Infirmary	
Duration of Study:	12 months	
Primary Objective:	Does magnesium administration enhance the biochemical response to thiamine as measured by the activity of the enzyme transketolase in red blood cells?	
Secondary Objective:	
 
What is the effect of the administration of thiamine alone,
 
Magnesium alone, or both together on
 
Plasma lactate concentrations
 
Biomarkers of ageing
 
	
Primary Endpoint:	Change in erythrocyte transketolase activity after treatment with - Thiamine - Magnesium - Thiamine plus magnesium	
Rationale:	Chronic alcoholics have a 30-80% incidence of thiamine deficiency causing Wernicke's Encephalopathy (WE). Intravenous (IV) thiamine replacement is standard practice in the treatment of alcoholic patients presenting to the Accident & Emergency (A&E) department, however routine co-supplementation with magnesium (administered IV as magnesium sulphate ), a co-factor for thiamine in some metabolic processes, e. g. on the activity of the enzyme transketolase in red blood cells, is not routine practice in the treatment of these patients. Without correction of concomitant magnesium deficiency there may be impaired utilisation of thiamine resulting in a failure to treat WE. This study is designed to determine if administration of Magnesium to alcoholic patients affects red cell transketolasae by itself, or only acts to increase the effect of thiamine on the activity of this enzyme.	
Methodology:	Open label, randomised controlled study	
Sample Size:	120	
Screening:	Confirmation of chronic alcoholism (FAST questionnaire. GMAWS score)	
Registration/Randomisation:	Randomisation will be performed using individually numbered opaque envelopes.	
Main Inclusion Criteria:	Chronic alcohol dependence	
Main Exclusion Criteria:	Known chronic renal failure	
Product, Dose, Modes of	Participants will be randomised to:	
Administration:	• Arm 1:Thiamine	
	
 
Arm 2: Thiamine and magnesium sulphate
 
Arm 3: Magnesium sulphate with delayed thiamine where thiamine will be administered as Pabrinex.
 
	
Duration of Treatment:	Each infusion will be administered over 30 minutes	

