## 3.5 Assessment and management of risk

As above, there are three arms to this study. Our previous study examined the effect of thiamine and magnesium, as compared to thiamine alone, on TKA activity. This demonstrated a significant increase in TKA activity in the magnesium and thiamine group as compared to the thiamine group. It is therefore necessary to include the magnesium sulphate arm to this study to confirm this effect was not directly attributable to Magnesium separately, and to elucidate the degree of synergism that may exist between magnesium and thiamine.

Alcoholism is a disease of malnutrition. Dietary deficiencies develop over weeks, months and years. We appreciate that the two hour delay to Pabrinex administration, represents a delay to standard treatment in the Magnesium group (with delayed Pabrinex). However there is no evidence in the literature to indicate that a real time delay of two hours may disadvantage a patient, or that a single treatment of Pabrinex can reverse the chronic changes associated with Vitamin B1 (Thiamine) deficiency. It is our view therefore that a two hour delay will not disadvantage the patients randomised to this group. Indeed a 2 hour delay is not uncommon in the Emergency Department (ED) for any treatment due to the acuity and volume of patients attending a busy inner city ED. All patients attending the ED should be treated and discharged within the 4 hour window, as dictated by the national access target for emergency care.

Patients will be identified at triage in order to ensure adequate time to recruit, consent and obtain repeat samples at the 2 hour time interval post administration of treatment whilst still meeting national targets. Eligible patients may therefore be seen earlier in their patient journey which may offset potential delays due to study involvement. The net effect will be that patients randomised to the Magnesium group, will therefore receive their Pabrinex at approximately the same point in their patient journey, as if the study were not ongoing.

Magnesium sulphate and pabrinex are routinely administered to this patient group in the ED at GRI.

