# 4 TRIAL PROCEDURES

#### 4.1 Patient identification and consent

Patients will be identified by ED staff on presentation and will be determined to be alcohol dependent (Fast Alcohol Screening Test questionnaire) or in alcohol withdrawal as determined by the GMAWS scale (appendix) as per standard practice. Patients will then be

approached about the study by a trained and appropriately delegated member of the ED team who will provide a Patient Information Sheet and go through the purpose of the study and what it would require of them, and have any questions they may have addressed. Patients will then be given up to 30 minutes to decide whether they wish to take part. If they agree to participate patients will then be asked to sign a study consent form by a member of ED/research team. Eligibility to participate in the study will be confirmed by appropriately trained and delegated medical staff.

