## Part 4: Administration of delayed Pabrinex (Arm 2 only)

For patients randomised to Arm 2, (IV magnesium sulphate and delayed thiamine), Pabrinex will be administered after the second blood samples have been taken, approximately 2 hours (+/- 30mins) after completion of magnesium sulphate infusion.

Case report forms will be updated as appropriate.

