# 6. DRUG INFORMATION

Patients who are eligible for the study will be randomised to receive one of the following arms:

- Arm 1: IV thiamine (Pabrinex)
- **Arm 2:** IV magnesium sulphate followed by delayed thiamine (Pabrinex) administered after completion of post-intervention assessments.
- Arm 3: IV thiamine (Pabrinex) and IV magnesium sulphate

In Arm 3 IV Pabrinex and IV magnesium sulphate will be administered concurrently. There is limited data available on Y-site compatibility for Pabrinex and magnesium sulphate infusions

however, it has been standard practice at GRI to administer in this way for a number of years.

All study drug administration will be completed within the ED where full resuscitation facilities are available.

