## 6.4.3 Administration

Magnesium sulphate will be administered an intravenous infusion. Two grams of magnesium sulphate will be added to 100ml of sodium chloride 0.9% and administered IV over 30 minutes. The infusion should be inspected prior to administration to ensure absence of particulates. No dose modifications are permitted. The infusion rate may be adjusted as per standard practice.

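### Does section 3.5 understate the delay to Pabrinex in Arm 2 by calling it two hours?

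*Combined protocol and SAP*

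**What the plan says.** Section 3.5 (Assessment and management of risk) concedes the delay in Arm 2: "We appreciate that the two hour delay to Pabrinex administration, represents a delay to standard treatment". It then argues that "there is no evidence in the literature to indicate that a real time delay of two hours may disadvantage a patient" and concludes: "It is our view therefore that a two hour delay will not disadvantage the patients randomised to this group". It adds that waits of this length are common in the department for any treatment, that the deficiency is long-standing, and that recruiting at triage brings patients forward. On the last ground it expects Arm 2 patients to receive Pabrinex at about the point they would have reached outside the study. The delay statements carry no starting point and no tolerance.

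The schedule is set elsewhere. Section 4.3, Part 4, gives Arm 2 its Pabrinex once the second blood samples are taken, "approximately 2 hours (+/- 30mins) after completion of magnesium sulphate infusion". The synopsis says "Each infusion will be administered over 30 minutes", and section 6.4.3 agrees for magnesium: "magnesium sulphate will be added to 100ml of sodium chloride 0.9% and administered IV over 30 minutes". In Arm 1, Pabrinex is the infusion given in Part 2 of section 4.3. For the combined arm, section 6 says "In Arm 3 IV Pabrinex and IV magnesium sulphate will be administered concurrently".

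**The concern.** Two hours without standard treatment reads naturally as the whole time an Arm 2 patient goes without Pabrinex while patients in the other arms have it. On the written schedule that time is longer. The 30-minute magnesium infusion comes first, and the wait starts only when it ends. Two hours would then be the shortest delay allowed between arms, not the expected one.

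What would be at stake is the ethical justification for one arm. Two statements in section 3.5 are tied to the figure: that the literature shows no disadvantage, and that such a delay is common in the department. If the schedule produces two and a half hours, and allows three, both statements would have been made for a shorter delay than patients experience. Section 3.5 also relies on the 4-hour emergency care target, and a longer Arm 2 pathway leaves less room within it.

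**Working it through.** **Inputs**

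- Magnesium infusion: 30 min (synopsis; section 6.4.3).
- Wait from the end of magnesium to Pabrinex in Arm 2: 120 min, limits 90 and 150 (section 4.3, Part 4).
- Pabrinex infusion: 30 min (synopsis; section 6.3.3).
- Pabrinex start in Arms 1 and 3: time 0, the start of study treatment (section 4.3, Part 2; section 6).
- Time to decide on consent: 0 to 30 min, from section 4.1: "Patients will then be given up to 30 minutes to decide whether they wish to take part".
- Emergency department window: 240 min (section 3.5).

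**Step 1: reproduce the two hours.** Counting from the end of magnesium, the delay is the wait itself: 120 min (90 to 150). The stated figure is reproduced as the nominal value.

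**Step 2: delay relative to Arms 1 and 3.** Delay = magnesium infusion + wait.

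| | Infusion | Wait | Delay | Ratio to 120 |
|---|---|---|---|---|
| Early limit | 30 | 90 | 120 min | 1.00 |
| Nominal | 30 | 120 | 150 min | 1.25 |
| Late limit | 30 | 150 | 180 min | 1.50 |

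Comparing the ends of the Pabrinex infusions instead of the starts gives the same result, because 30 min is added on both sides. Section 6.4.3 allows the infusion rate to be adjusted, so 30 min is itself nominal. With an assumed magnesium infusion of 15 to 60 min, the nominal delay would run from 15 + 120 = 135 min to 60 + 120 = 180 min.

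**Step 3: the 4-hour window.** Timed steps in Arm 2 = decision + magnesium + wait + Pabrinex.

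- Minimum: 0 + 30 + 90 + 30 = 150 min, leaving 240 - 150 = 90.
- Nominal wait, no decision time: 0 + 30 + 120 + 30 = 180 min, leaving 60.
- Nominal wait, full decision time: 30 + 30 + 120 + 30 = 210 min, leaving 30.
- Maximum: 30 + 30 + 150 + 30 = 240 min, leaving 0.

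What is left must cover triage, eligibility checks and baseline samples, for which the protocol gives no times. The late limit is tight, but the figures do not show a breach.

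**Step 4: does the delay enter the analysis?** Section 4.4.1 defines the primary outcome as the change in transketolase activity from before treatment to 2 hours (+/- 30 min) after it. Section 4.3, Part 4, and section 6 both place Arm 2's Pabrinex after the second assessments. The outcome is therefore measured before the delayed dose, whichever clock is used to describe the delay. The sample size in section 8.1 uses a difference of 0.16 and the pilot standard deviation, and no timing.

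**Step 5: which clock does section 3.5 use?** Its next paragraph refers to repeat samples taken 2 hours after treatment is given. Part 4 attaches the delayed Pabrinex to those samples and counts from the end of magnesium. Read together, two hours is shorthand for that post-treatment wait. Section 3.5 compares it with standard care in the department and gives no between-arm figure. The protocol does not state the usual time to Pabrinex, so the delay relative to usual care cannot be calculated.

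**The case for a change.** The strongest case for a change is that section 3.5 is where the protocol justifies holding back standard treatment, and a reader of that section alone would not learn that three hours behind the other arms is allowed. The words used there describe time without treatment, not time since an infusion ended. Even on the favourable reading the 30-minute tolerance is missing. Identification at triage may offset the delay relative to usual care, but it does nothing to the gap between arms. The remedy would be a phrase.

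Part of this stands. The starting point and tolerance are not attached to the delay statement, and the nominal delay relative to Arms 1 and 3 is 150 minutes.

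The rest does not carry it to a change of plan. Two hours agrees with Part 4 on the clock that Part 4 itself uses, so no sum is wrong. The remark on common waits concerns the department in general and is not a description of Arm 2. The arguments from chronic deficiency and from triage do not depend on the figure. Nothing in the documents shows that the no-disadvantage view holds at two hours and fails at two and a half, and this note takes no position on what delay is acceptable.

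**Conclusion.** The arithmetic behind the concern is right: Arm 2 starts Pabrinex nominally 150 minutes (120 to 180) after Arms 1 and 3, 30 minutes more than the two hours in section 3.5. This rests on a 30-minute magnesium infusion and on Arms 1 and 3 starting Pabrinex when study treatment starts. It is an unstated starting point in a risk narrative, not a contradiction in the schedule, because the nominal wait after magnesium is the same two hours.

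Staff work from Part 4 and section 6.4.3, which give the order, starting point and tolerance. No endpoint, analysis or sample size is affected, and no breach of the 4-hour window is shown. Clearer wording would alter neither what the trial does nor what it can conclude, so no change is called for. If section 3.5 is reopened for another reason, its figure can be reconciled with Part 4 and section 6.4.3. The intended timing, and the delay to which the no-disadvantage statement applies, are for the sponsor to confirm.

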# 4 TRIAL PROCEDURES

#### 4.1 Patient identification and consent

Patients will be identified by ED staff on presentation and will be determined to be alcohol dependent (Fast Alcohol Screening Test questionnaire) or in alcohol withdrawal as determined by the GMAWS scale (appendix) as per standard practice. Patients will then be

approached about the study by a trained and appropriately delegated member of the ED team who will provide a Patient Information Sheet and go through the purpose of the study and what it would require of them, and have any questions they may have addressed. Patients will then be given up to 30 minutes to decide whether they wish to take part. If they agree to participate patients will then be asked to sign a study consent form by a member of ED/research team. Eligibility to participate in the study will be confirmed by appropriately trained and delegated medical staff.

## 4.2 Randomisation

Randomisation will be performed in advance by the study statistician and opaque envelopes detailing the subject number and treatment allocation prepared. Patients will be sequentially assigned a subject number once eligibility is confirmed and the corresponding treatment assignment envelope opened. The opened enveloped will be retained and attached to the patient's case report form (CRF)

## 4.3 Trial assessments

Patients who have consented to participate in the study will have all study procedures carried out in a single visit. Where the procedure differs for the respective groups this will be indicated in the schedule below

#### Part 1: Baseline Assessments

- Medical history
- Pregnancy test for female participants of child-bearing potential.
- Randomisation
- Blood samples for biochemistry
  - **Standard care:** FBC, U&E, LFT, Gamma GT, CRP, serum Magnesium, glucose and lactate, random cortisol and nutritional markers
  - Study specific: erthyrocyte TKA, thiamine and magnesium trace elements copper, manganese, and zinc and vitamin A, B1, B2, B6, B9, B12 C, D, E and K
- Blood sample eGFR and blood glucose
- Weight
- Physical examination

#### Part 2: Administration of study medicines

Patients will be randomised to one of the following regimes and infusions administered:

• Arm 1: IV thiamine (Pabrinex)

- Arm 2: IV magnesium sulphate and delayed Pabrinex
- Arm 3: IV thiamine (Pabrinex) and IV magnesium sulphate

#### Part 3: Post-intervention Assessments

Patients in all groups will then have repeat blood samples 2 hours (+/- 30mins) for biochemistry

- serum magnesium, glucose, cortisol and lactate
- erthyrocyte TKA, thiamine and magnesium,
- trace elements copper, manganese, copper and zinc
- vitamins A, B1, B2, B6, B9, B12, C, D, E and K

## Part 4: Administration of delayed Pabrinex (Arm 2 only)

For patients randomised to Arm 2, (IV magnesium sulphate and delayed thiamine), Pabrinex will be administered after the second blood samples have been taken, approximately 2 hours (+/- 30mins) after completion of magnesium sulphate infusion.

Case report forms will be updated as appropriate.

# 4.4 Study Outcome Measures

#### 4.4.1 **Primary Outcome Measure**

- The relative change in TKA pre- and 2 hours (+/- 30mins) post-administration of
  - IV thiamine
  - IV magnesium sulphate
  - IV thiamine + IV magnesium sulphate

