Statistical Analysis:	A three group study was designed to detect a minimum biochemically significant difference of 0.16 in the change from baseline between the groups, with 80% power and a 5% significance level. total sample size = 120. Methodology: One way ANOVA	

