# 1. INTRODUCTION

# 1.1 Background

Alcohol related conditions account for up to 40% of weekday Emergency Department attendances. II Socioeconomic deprivation has a well-proven association with rates of alcoholism in the community. Glasgow Royal Infirmary serves the north and east of Glasgow, parts of which have been designated by the WHO to be among the most deprived areas in Europe.

Between 30-80% of chronic alcoholics have thiamine deficiency. The incidence of Korsakoff's psychosis has been noted to be steadily increasing in the East End of Glasgow since 1990. Wernicke-Korsakoff Psychosis has also been shown to be related to Thiamine deficiency. Magnesium ( $Mg^{2+}$ ) is known to be an essential cofactor for Thiamine, though its effect on the enzyme transketolase, in the Pentose Phosphate Shunt and as such is advocated by core Emergency Medicine texts in the treatment of alcoholic or malnourished patients.

The aim of this project is to further clarify the effect of concurrent magnesium supplementation with thiamine administration on Red Cell Transketolase (TKA) Activity in a cohort of alcoholic patients admitted through ED. Patients will be determined to be alcohol dependent from history (FAST questionnaire) or in alcohol withdrawal as determined by the GMAWS scale (appendix).

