Current evidence consists mainly of case reports and clinical observations. Given the weight of biochemical evidence available it is surprising that this role has not been clarified in a clinical study context. A comprehensive search of the literature revealed only one clinical study (co-written by this author) comparing effects of thiamine alone versus thiamine and magnesium sulphate on Red Cell Transketolase (TKA) in alcoholic patients.  In this study, a more rapid recovery of the thiamine dependent enzyme Red Cell TKA occurred, when 2 grams magnesium sulphate was delivered simultaneously with thiamine than in a similar patient group treated with thiamine alone, however this study was not fully controlled.

The Scottish Intercollegiate Guidelines Network (SIGN) also identify the dosage and duration of Thiamine administration as an area of research to be encouraged. The role of Mg2+ as an essential cofactor has a definite relevance to this question as Mg2+ may be influential in determining efficacy.

In this study we would like to extend out previous work by randomising alcoholic patients to treatment with either thiamine alone, magnesium sulphate alone (with delayed thiamine), or

concurrent administration of thiamine plus magnesium sulphate, to determine whether treatment with magnesium sulphate has any effect on its own on red blood cell transketolase activity, or only acts to increase the effect of thiamine.

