# 3.2 Inclusion criteria

- Written informed consent
- Male or non-pregnant or breastfeeding females ≥18 years of age For women of childbearing potential a negative pregnancy test will be required prior to treatment.
   (Women of non-childbearing potential are defined as those defined as women who are post-menopausal or permanently sterilised (e.g. hysterectomy, tubal occlusion, bilateral salpingectomy).
- Chronic alcohol dependence as confirmed by
  - FAST questionnaire
  - GMAWS scale

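### Baseline TKA is used only through the change score; adding it as a prespecified covariate, on one stated scale, could raise power at no cost in patients or samples

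*Combined protocol and SAP*

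**What the plan says.** - **Sampling.** Section 4.3 lists TKA among the study-specific baseline bloods ("erthyrocyte TKA, thiamine and magnesium trace elements copper, manganese, and zinc"). After treatment, "Patients in all groups will then have repeat blood samples 2 hours (+/- 30mins) for biochemistry", and TKA is again on the list. Each patient should therefore have a pair of values.
- **Outcome.** Section 4.4.1 gives "The relative change in TKA pre- and 2 hours (+/- 30mins) post-administration of" each treatment. The synopsis endpoint is "Change in erythrocyte transketolase activity after treatment with" each treatment, without the word relative. Sections 8.1 and 8.2 speak of change from baseline. No formula is given anywhere.
- **Analysis.** The synopsis entry ends "total sample size = 120. Methodology: One way ANOVA". Section 8.2, although headed as the statistical analysis plan, holds only pilot descriptives and a repeat of the sample size paragraph. It names no model and no covariate.
- **Sample size.** Sections 8.1 and 8.2 use a difference of 0.16, the higher pilot standard deviation (0.2176, the combined group, n = 18), 80% power and a 5% level. They arrive at 37 per arm and plan 120 in total. Neither 0.16 nor 0.2176 carries a unit or scale.

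**The concern.** Subtracting baseline, or dividing by it, is not the same as adjusting for it. If change still depends on the starting value within an arm, a one-way ANOVA leaves that variation in the error term. A linear model with baseline as a covariate removes it, from data already collected.

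The documents give some reason to expect such dependence. Section 1.1 states: "Between 30-80% of chronic alcoholics have thiamine deficiency". Section 1.2 reports from the earlier study that "a more rapid recovery of the thiamine dependent enzyme Red Cell TKA occurred" when magnesium was given with thiamine. Entry under section 3.2 requires "Chronic alcohol dependence as confirmed by" the FAST questionnaire and the GMAWS scale, but not thiamine deficiency. The sample can therefore mix deficient patients, who have room to respond, with replete patients, who have less. This is an inference; no correlation between baseline TKA and its change is reported.

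The undefined scale belongs to the same point because the covariate model cannot be written until it is settled. The three descriptions of the outcome do not contradict one another, since a change from baseline may be relative. But the reader cannot tell which change the 0.16 refers to.

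**Working it through.** **Inputs from the documents.** Difference 0.16, SD 0.2176, 5% level, 37 per arm (sections 8.1 and 8.2); 40 per arm randomised (section 3.1).

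**Assumptions.** Omnibus F test, third arm mean midway between the other two, the same SD in every arm. The within-arm correlation rho of change with baseline is not in the documents and is shown over a range. Only its square matters, so its sign does not affect power.

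**1. The plan's own figure.** With means 0, 0.08 and 0.16 the noncentrality is

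lambda = n × 2 × 0.08² / 0.2176² = 37 × 0.0128 / 0.04735 = 10.00, on 2 and 108 degrees of freedom.

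Power is 80.4% at n = 37 and 79.2% at n = 36, so the stated 37 per arm reproduces. If all 40 per arm are evaluable, power is 83.6%.

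**2. Baseline added, same rho in all arms.** Residual variance is multiplied by (1 − rho²), then by 1 + 1/(3n − 5) for estimating the slope, and one error degree of freedom is lost. At n = 37 the slope factor is 1 + 1/106. For rho = 0.3:

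lambda = 10.00 / (0.91 × 1.0094) = 10.89, on 2 and 107 degrees of freedom, power 83.8%.

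| rho (assumed) | Power, 37 per arm | Power, 40 per arm |
|---|---|---|
| Unadjusted ANOVA | 80.4% | 83.6% |
| 0 | 80.0% | 83.3% |
| 0.1 | 80.4% | 83.7% |
| 0.2 | 81.7% | 84.9% |
| 0.3 | 83.8% | 86.8% |
| 0.5 | 90.5% | 92.7% |

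Break-even is near rho = 0.1. The cost if baseline is useless is 80.4 − 80.0 = 0.4 points; counting only the lost degree of freedom would put it below 0.1.

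**3. Baseline predictive only in the two thiamine arms.** This fits the biological argument better, because the magnesium-first arm has had no thiamine when the 2-hour sample is taken. By simulation (20,000 runs, 37 per arm, lognormal baseline with CV 30%), a common-slope model gives 81.3% at rho 0.3 and 83.5% at rho 0.5, against 80.2% unadjusted.

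**4. If 0.16 and 0.2176 are proportional changes.** Same simulation set-up, change independent of baseline, baseline CV 20% to 50%:

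| Analysis | Power |
|---|---|
| ANOVA of relative change | 80.1–80.9% |
| Relative change, log baseline as covariate | 79.8–80.6% |
| Log 2-hour TKA on log baseline | 78.5–79.9% |

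With rho −0.3 the two adjusted models give 83.5–84.3% and 82.5–83.3%; with rho −0.5 they give 90.3–91.0% and 89.2–89.8%. Keeping relative change as the outcome and adding log baseline is therefore slightly the better choice on this scale.

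**5. Validity.** The simulated type I error of the adjusted models was 4.7% to 5.3%.

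**The case against.** The planned ANOVA is valid and correctly sized, so what remains is a preference for one sound analysis over another. The gain rests on a correlation the documents do not report. The largest figure, 90.5%, needs rho 0.5 in all three arms, while the thiamine-deficiency argument supports an effect only in the arms that have had thiamine, where the gain is about 1 to 3 points. All of this stands, and it sets how the size should be read.

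The starting power may also be higher than 80.4%. At 37 per arm, changing one assumption at a time, it is 91.5% with the pooled pilot SD of 0.186, and 90.7% if the magnesium-alone mean equals that of one other arm (93.0% adjusted, rho 0.3). The contrast closest to the primary objective, combined against thiamine alone, has 87.7% with an unadjusted two-sample t test. A higher start shrinks the gain but does not remove it.

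There are two practical objections. Section 13 requires an amendment for any protocol change, with ethics and R&D approval, so the cost is more than an edit; it is still small beside a trial of 120. For lactate no SD or correlation is available, so no gain can be calculated. The reasoning does carry over, because lactate too is measured at baseline and at 2 hours.

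**Conclusion.** The point holds as an efficiency improvement worth considering. It is not an error in the analysis or the sample size.

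On the biologically better supported case (baseline predictive in the thiamine arms only, rho 0.3 to 0.5) the gain is about 1 to 3 points of power at 37 per arm. If baseline predicts change equally in all arms, it is about 3 to 10 points over the same range. If baseline carries no information, about 0.4 points are lost.

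These figures assume the omnibus F test, SD 0.2176 in every arm, a difference of 0.16 and the third mean midway. Rho is an assumption throughout, so no single gain can be promised. Stating the scale is needed whether or not the covariate is adopted, since the primary outcome cannot be computed without ambiguity from the present text.

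**What to change.** 1. Check in the pilot data whether 0.16 and 0.2176 are absolute or proportional changes. State the answer, with the assay unit, in sections 8.1 and 8.2.
2. Use that one definition in the synopsis (endpoint and statistical analysis), section 4.4.1 and sections 8.1 and 8.2.
3. Replace the one-way ANOVA with a linear model on randomised arm, with baseline TKA as a prespecified covariate:
   - **If absolute:** model 2-hour TKA on arm and baseline TKA, and remove the word relative from section 4.4.1.
   - **If proportional:** define relative change as (2-hour − baseline)/baseline, keep it as the outcome, and add log baseline TKA as the covariate. The 0.16 and 0.2176 then stand unchanged. Log 2-hour TKA on log baseline is acceptable, but both figures would need restating and about 1 to 2 points of power are lost if change is independent of baseline.
4. Apply the same approach to lactate in section 4.4.2.

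**Cost.** A look-up in existing pilot data, an amendment of wording under section 13, one error degree of freedom, and about 0.4 points of power if baseline proves useless. No new patients or samples are needed, and N = 120 need not change.
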